1.1 Background

In addition to significant morbidity from RA morbidity, the risk of myocardial infarction is increased nearly 2-fold in the setting of RA.(Meune et al., 2010; Solomon et al., 2006) Rheumatoid arthritis induced activation of systemic inflammatory pathways and endothelial dysfunction has been implicated in this increased risk.(Sattar et al., 2003) Inflammation mediates many aspects of disease pathogenesis in atherosclerosis, involving diverse cell types and mediating signals.(Hansson, 2005) Platelets have been implicated in atherosclerosis because of their pro-inflammatory and thrombogenic effects.(Gawaz et al., 2005) Moreover, pathological and clinical studies demonstrated the importance of platelet activity in cardiovascular events. It is likely that increased platelet reactivity in patients with RA contributes to the increased risk of myocardial infarction and also contributes to the joint inflammation as well.

1.2 Investigational Agent

This study is looking at the investigational agent ticagrelor. Subjects who are already receiving MTX at stable doses of 10 to 25 mg weekly for at least 12 weeks will receive 90 mg of ticagrelor given orally bid. Ticagrelor is an oral, direct-acting, reversibly binding P2Y₁₂ receptor antagonist, that is approved for the treatment of patients with acute coronary syndrome and prior myocardial infarction. In addition to its antiplatelet effects, ticagrelor can inhibit adenosine cell uptake, likely through inhibition of the equilibrative nucleoside transporter 1. Ticagrelor also significantly increases coronary blood flow velocity via an adenosine mediated mechanism.

1.3 Preclinical Data

Methotrexate (MTX) is the anchor drug in the treatment of rheumatoid arthritis (RA) although many patients will not achieve a complete response to MTX alone. (Weinblatt, 2013) In general, the onset of action of MTX is delayed (onset by 2-3 months) although generally most physicians will not add another agent for the treatment of RA until three months after the patient started MTX therapy and has not achieved a significant clinical response. (Weinblatt, 2013) In prior studies we have shown (Chan and Cronstein, 2013) that many, if not most, of the anti-inflammatory effects of MTX are mediated by an increase in extracellular levels of adenosine, a potent anti-inflammatory agent acting at its receptors (primarily A_{2A} and A₃). We postulate that insufficient levels of adenosine to suppress inflammation are reached in many patients not achieving an adequate response to MTX therapy; generally speaking these patients will be prescribed biologic agents (e.g. anti-TNF agents). Because ticagrelor blocks adenosine uptake (Cattaneo et al., 2014) and adenosine contributes to the therapeutic effects of ticagrelor we further hypothesize that ticagrelor will enhance the anti-inflammatory effects of MTX in the treatment of RA. Thus, if addition of ticagrelor enhances MTX response then it may be possible for patients to avoid use of a biologic therapy.

1.4 Dose Rationale

Ticagrelor 90 mg twice daily will be used in this study. This dose was chosen based on ticagrelor's antiplatelet effect at this dose and use in other indications (acute coronary syndrome, prior myocardial infarction). In addition, there is a concentration-dependent response for ticagrelor in vitro in terms of conservation of added adenosine to whole blood. There is also an effect on adenosine induced coronary blood flow of a 180mg loading dose of ticagrelor in healthy subjects (Wittfeldt 2013) and after 90mg in ACS patients (Alexopolous 2013). This effect is mediated by inhibition of the adenosine transporter ENT1 (type 1 equilibrative nucleoside transporter), which provides protection for adenosine from intracellular metabolism, thus increasing its concentration and biological activity. Study medication will be taken orally, twice a day. Safety and tolerability will be monitored closely during the study. The 30-day study duration is considered sufficient to investigate acute safety and efficacy in ticagrelor in RA.

CONFIDENTIAL

1.5 Research Risks & Benefits

1.5.1 Risk of Study Drug

Ticagrelor can cause bleeding that can be serious and sometimes lead to death. Instances of serious bleeding, including internal bleeding, may require blood transfusions or surgery. Subjects taking ticagrelor may bruise and bleed more easily and be more likely to have nosebleeds. Bleeding will also take longer than usual to stop. Subjects who experience any of these symptoms will be informed to call their study doctor immediately and call 911 in the event of an emergency.

Patients who are taking ticagrelor are also at a greater risk of dyspnea. If ticagrelor must be temporarily discontinued (e.g., to treat bleeding or for significant surgery) it should be restarted as soon as possible. Because the primary route of ticagrelor elimination is hepatic metabolism, patients with severe hepatic impairment should not use ticagrelor.

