1.5.3 Potential benefits

The benefits of ticagrelor in patients with RA are currently unknown.

2 Study Objectives

We propose to measure platelet activity in subjects with RA and OA and perform a preliminary clinical study in patients with rheumatoid arthritis that have active disease despite MTX therapy. Subjects will receive ticagrelor added to MTX for 30 days. The primary outcome is improvement in the Disease Activity Score for 28-joint counts (DAS28, with scores ranging from 2 to 10 and higher scores indicating more disease activity) at 30 days.

CONFIDENTIAL

3 Study Design

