4.2 Exclusion Criteria

Exclusion Criteria (RA cohort):

- History of sensitivity to study medications or any of their excipients
- Previous intolerance to MTX
- Current treatment with antiplatelet therapy
- Absolute indication for anti-platelet therapy
- Need for chronic oral anticoagulant therapy
- Severe hepatic impairment (eg, ascites and/or clinical signs of coagulopathy)
- Renal failure (eGFR <30 or requiring dialysis) by history
- A known bleeding diathesis, hemostatic or coagulation disorder, or prior major bleeding
- Prior stroke
- Active pathological bleeding
- History of intracranial haemorrhage

CONFIDENTIAL

- Life expectancy <12 months based on investigator's judgement
- Patients considered to be at risk of bradycardic events (e.g., known sick sinus syndrome or second or third degree atrioventricular [AV] block) unless already treated with a permanent pacemaker
- Anemia (hematocrit < 27%) by history
- Platelet count < 100,000/ml by history
- Concomitant use of strong CYP 3A inhibitors or inducers
- History of thrombocytopenia or neutropenia
- Pregnant or nursing women, or females with a positive urine and/or serum pregnancy test at screening/baseline
- Females of child bearing potential not using acceptable method of birth control prior to or during study
- Concern for inability of the patient to comply with study procedures and/or follow-up (eg, alcohol or drug abuse)

Exclusion Criteria (OA cohort):

- History of sensitivity to study medications or any of their excipients
- Current treatment with antiplatelet therapy
- Absolute indication for anti-platelet therapy
- Need for chronic oral anticoagulant therapy
- Severe hepatic impairment (eg, ascites and/or clinical signs of coagulopathy)
- Renal failure (eGFR <30 or requiring dialysis) by history
- A known bleeding diathesis, hemostatic or coagulation disorder, or prior major bleeding
- Prior stroke
- Active pathological bleeding
- History of intracranial haemorrhage
- Life expectancy <12 months based on investigator's judgement
- Anemia (hematocrit < 27%) by history
- Platelet count < 100,000/ml by history
- History of thrombocytopenia or neutropenia
- Pregnant or nursing women, or females with a positive urine and/or serum pregnancy test at screening/baseline
- Females of child bearing potential not using acceptable method of birth control prior to or during study
- Concern for inability of the patient to comply with study procedures and/or follow-up (eg, alcohol or drug abuse)

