4.5 Early Withdrawal of Subjects

4.5.1 Patient Withdrawal

Patients may withdraw from the study at any time and for any reason. Reason for study withdrawal will be documented and may include the following reasons:

- Patient choice;
- At the discretion of the Investigator;
- Development of a contraindication to ticagrelor or MTX;
- Development of a bleeding diathesis, hemostatic or coagulation disorder, or major bleeding;
- Pregnancy;
- Death.

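### Section 1.5.1 sets prompt restart as the default after ticagrelor is paused for bleeding, with no condition that the bleed has resolved; separately, Section 4.5.2 leaves patients stopped for an SAE out of its encouragement to complete visits

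*Combined protocol and SAP*

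**What the plan says.** Section 1.5.1 (Risk of Study Drug) contains the document's only restart instruction: "If ticagrelor must be temporarily discontinued (e.g., to treat bleeding or for significant surgery) it should be restarted as soon as possible". The same section warns that bleeding on ticagrelor can be serious or fatal and is slow to stop, and tells patients with symptoms to call the study doctor at once.

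The RA exclusions in Section 4.2 include "A known bleeding diathesis, hemostatic or coagulation disorder, or prior major bleeding", "Active pathological bleeding" and "Absolute indication for anti-platelet therapy". Section 1.5.3 states: "The benefits of ticagrelor in patients with RA are currently unknown".

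Section 4.5.1 introduces its withdrawal list with "Reason for study withdrawal will be documented and may include the following reasons". The list includes "Development of a contraindication to ticagrelor or MTX", "Development of a bleeding diathesis, hemostatic or coagulation disorder, or major bleeding" and the investigator's discretion.

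Section 4.5.2 encourages patients taken off study drug to stay in the study and attend all visits, but excepts those whose stop was due to an SAE. It requires additional follow-up for patients who withdraw because of an AE or SAE, and Section 9.2 follows ongoing SAEs to their outcome.

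**The concern.** Prompt restart is a sensible default where a gap in antiplatelet cover is itself dangerous. In this trial, patients with an absolute need for such cover are excluded and no benefit in RA is established. The protocol therefore identifies no harm from a longer pause that would offset the bleeding risk of early re-exposure, yet its one stated default favours speed. What is at stake is the safety of any patient who bleeds on drug, above all one with a non-major bleed, which the withdrawal list does not specifically name.

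The Section 4.5.2 exception raises a separate question about data. The primary outcome is DAS28 at 30 days in a single-arm before-and-after comparison. If Day 30 scores are lost because of the exception, they are lost selectively, in patients with serious events. The two points can meet in one patient: someone stopped permanently for a serious bleed would not be covered by the encouragement to complete Day 30.

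**Working it through.** The plan gives no figure for restarts or for bleeding, so the main check is a comparison of texts. The arithmetic only sizes the cost of the fix and the Day 30 effect.

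**1. Is restart conditional anywhere?**
- Section 1.5.1: restart is the default after a temporary stop, with bleeding as the first example. No condition on resolution is stated, and nobody is named to judge it.
- Section 4.2: active bleeding and prior major bleeding bar entry. These criteria apply at enrolment and are not stated as restart conditions.
- Section 4.5.1: major bleeding and a new contraindication are possible reasons for withdrawal, under wording that permits and does not require.
- Section 4.5.2: covers follow-up and staying in the study, not restarting drug.
- Section 5: covers administration, compliance, concomitant medication and supply. No restart rule.
- Section 9: covers definition, recording, reporting and monitoring of events. Section 9.5.1 has the investigator suspend enrolment after any severe adverse event pending discussion with the IRB. That governs enrolment, not the dosing of the patient concerned.

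No section supplies the missing condition.

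**2. Exposure given up by a stricter rule**
- Inputs: two doses a day for 30 days (Section 5.1) and 25 RA completers (Section 4.3).
- Planned doses per patient: 2 × 30 = 60. For 25 patients: 25 × 60 = 1,500.
- A patient who bleeds on drug has taken at least one dose, so the most that can be lost is 60 − 1 = 59 doses, or 59/1,500 = 3.9% of the planned total.
- With assumed permanent stops at day 5, 15 or 25, the loss is 50, 30 or 10 doses: 3.3%, 2.0% or 0.7%.

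**3. Day 30 DAS28 lost after an SAE**
- Inputs: planned mean improvement of 1.2 (Section 8) and 25 RA patients. Assumption: the lost patient's true change is c, which the documents do not give.
- Mean with that patient included: (24 × 1.2 + c)/25. Mean in completers: 1.2. Difference: (1.2 − c)/25.
- c = 0: the full mean is 28.8/25 = 1.152, a shift of 0.048.
- c = 0.6: 0.6/25 = 0.024. c = 1.2: no shift.
- If the patient is replaced so that 25 still complete, the full group is 26. With c = 0 the mean is 1.2 × 25/26 = 1.154, a shift of 0.046.

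**The case against.** The strongest reply is that the harmful reading is the less natural one. The sentence concerns a temporary stop made in order to treat bleeding, so the soonest possible restart most naturally means once treatment allows. It sits in a description of risks, not in the dosing or withdrawal sections. A physician is involved, because patients with symptoms are told to call. Serious cases have a route out through Section 4.5.1, which names major bleeding, contraindication and investigator discretion, and Section 9.5.1 adds review with the IRB after severe events. All of this stands, and it leaves mainly non-major bleeds and the permissive wording of the withdrawal list. It does not remove the point: the wording directs a restart, and nothing elsewhere conditions it.

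A reader might go further and infer that the protocol orders re-dosing of a patient who is still bleeding, or that Section 1.5.1 contradicts Sections 4.2 and 4.5.1. The documents support neither. The sentence covers temporary stops only, the entry criteria apply at entry, and withdrawal after major bleeding remains open to the investigator.

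On Section 4.5.2, a reader might infer that SAE patients are barred from Day 30 or go without follow-up. Neither is so. Table 1 and Section 6.3 schedule Day 30 for the RA cohort with no exemption for patients off drug, and safety follow-up is required. What these patients lack is the explicit encouragement that the others receive. Nor is this a power problem: Section 4.3 aims for 25 RA completers within a maximum total accrual of 60, and Section 8 already allows for 20% attrition.

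**Conclusion.** The point holds as a cheap safety improvement. Section 1.5.1 states a default that suits this population poorly, and no section ties restart to resolution of the bleed. It is an ill-fitting instruction, not a contradiction. How many patients it would affect cannot be estimated: the documents give no bleeding rate, an assumed rate of major bleeding would not measure premature restarts, and the number may be zero.

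The Section 4.5.2 point is separate and small. Its size, about 0.05 DAS28 points per lost patient against a planned improvement of 1.2, rests on the assumption of no change in that patient. It vanishes if the patient would have improved as much as the rest. The reason to act is that the loss would be selective and costs almost nothing to avoid.

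**What to change.** In Section 1.5.1, delete the restart sentence or replace it with wording such as: after a temporary stop for bleeding, restart only once the bleed has resolved and the investigator judges it safe; do not restart after major bleeding (see 4.5.1).

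In Section 4.5.2, remove the SAE exception from the stay-on-study sentence, so that patients stopped for an SAE are also encouraged to complete the Day 30 assessments. Encouragement leaves them free to decline.

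Both are wording amendments that add no visits or assessments. The downside is the small loss of exposure shown above, confined to patients who bleed and are not restarted.

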1.5.2 Risks of all study related procedures

Blood draw: Possible side effects from drawing blood include: faintness, inflammation of the vein, pain, bruising, or bleeding at the site of puncture. There is also a slight possibility of infection.

Risk of brachial artery reactivity test: There are no known risks associated with the procedures for measurement of flow-mediated vasodilation. Inflation of a blood pressure cuff for 5 minutes for transient arterial occlusion may be associated with local arm discomfort that is rapidly relieved upon deflation of the cuff. Rarely, cuff inflation can be associated with local bruising.

Nitroglycerin may be associated with transient headache and lightheadedness due to lower blood pressure. Due to its short half-life, side effects would be expected to last < 30 minutes. To minimize risk of hypotension, nitroglycerin will not be administered if resting systolic blood pressure is <100 mmHg.

Loss of privacy and confidentiality: As with participation in any research study, there is always a risk that confidential or private information can be compromised. To minimize this risk, the study team will de-identify your samples and replace your identifying information, such as your name, with a bar code label that will not be associated with any data related to you (for example, your birthday or street address).

Risk of Genetic Testing: Any type of genetic evaluation can generate information about your personal health risks and can cause or increase anxiety, damage family relationships, and/or compromise insurability, employability and can even lead to discrimination. In order to protect against loss of confidentiality, sensitive information will be kept on a secured database and the samples will be de-identified before they are used in research. Your name and identifiers will not be mentioned in publications or reports, thereby greatly reducing the possibility of psychological or social risks that could arise from knowledge of this genetic information, such as risk for your employability or insurability or the risk of discrimination.

1.5.3 Potential benefits

The benefits of ticagrelor in patients with RA are currently unknown.

2 Study Objectives

We propose to measure platelet activity in subjects with RA and OA and perform a preliminary clinical study in patients with rheumatoid arthritis that have active disease despite MTX therapy. Subjects will receive ticagrelor added to MTX for 30 days. The primary outcome is improvement in the Disease Activity Score for 28-joint counts (DAS28, with scores ranging from 2 to 10 and higher scores indicating more disease activity) at 30 days.

CONFIDENTIAL

3 Study Design

3.1 General Design

This is an open label study to assess the improvement in the Disease Activity Score for 28-joint counts (DAS28) with ticagrelor given at 90 mg twice daily in patients with RA who have active disease despite MTX therapy (as defined by the inclusion/exclusion criteria). There will also be a cross sectional analysis of baseline platelet activity in subjects with rheumatoid arthritis and osteoarthritis. Subjects in the OA cohort will not receive any study medication, and will only have one study visit.

Patients will receive 90 mg ticagrelor orally twice daily. The patients will receive drug for 30-days. Methotrexate will be by prescription as per standard of care and the dose will remain stable throughout the study duration.

A summary of the study design is noted in the Supplemental Figure of Study Design. Briefly, there are 2 major goals: 1) we would like to demonstrate the heightened cardiovascular risk in RA by comparing platelet activity, inflammation and endothelial function in baseline rheumatoid arthritis versus age- and sex-matched patients with osteoarthritis; and 2) we would like to demonstrate the effect of ticagrelor in rheumatoid arthritis by the pre- and post- measures of clinical RA severity, platelet activity, inflammation and endothelial function in rheumatoid arthritis before and after ticagrelor therapy.

3.2 Secondary Study Endpoints

The primary outcomes of this study are: (1) investigate the heightened platelet profile in subjects with RA versus those with osteoarthritis, and (2) demonstrate the improvement in the Disease Activity Score for 28-joint counts (DAS28, with scores ranging from 2 to 10 and higher scores indicating more disease activity) at 30 days. The DAS28 is a composite index of the number of swollen and tender joints, the erythrocyte sedimentation rate, and a patient-reported disease activity.(Prevo et al., 1995) A decrease in the DAS28 of 1.2 or more is considered to be a clinically meaningful improvement.(van Gestel et al., 1996)

3.3 Secondary Study Endpoints

Rheumatoid Arthritis Severity

To assess whether ticagrelor 90 mg twice daily for 30 days improves:

- American College of Radiology (ACR) 20, 50, and 70 responses, indicating 20%, 50%, and 70% reductions, respectively, in the number of both tender and swollen joints and equivalent improvement in at least three of five other criteria
- Responses on the Clinical Disease Activity Index (CDAI), which is a composite score of the sum of tender and swollen joints (28 joints) and the patient and physician global assessments (each scored with the use of a scale ranging from 0 to 10), and
- Responses on the Routine Assessment of Patient Index Data 3 (RAPID3), which is a composite score of the sum of physical function, pain and patient global estimate
- Functional outcomes, as measured with the use of the Multi-dimensional Health Assessment Questionnaire (MDHAQ)

Adenosine Activity

To assess whether ticagrelor for 30 days improves:

- Vascular endothelial dysfunction
- Endothelial function will be measured by brachial artery reactivity testing (BART) before and after 30 days of therapy because a) this measure has been shown to improve in response to short-term therapy in other inflammatory conditions,(Flammer et al., 2008; Gupta et al., 2008; Patti et al., 2011; Warnholtz et al., 2009) b) it is a validated noninvasive and minimal risk measure of cardiovascular health,(Liang et al., 1998; Sorensen et al., 1995) and c) it is predictive of incident cardiovascular events and mortality.(Celermajer et al., 1992)
- Adenosine receptor expression on PBMCs

CONFIDENTIAL

Platelet Activity

To assess whether ticagrelor for 30 days causes a greater decline in platelet activity than baseline using the following markers:

- ADP-induced platelet aggregation
- Vasodilator-stimulated phosphoprotein (VASP) index
- Monocyte – platelet aggregation

3.4 Primary Safety Endpoints

A safety objective of this study will be to assess the safety and tolerability of ticagrelor in participants with active RA despite MTX therapy. Bleeding events will be analyzed using accepted bleeding definitions (PLATO, ISTH and BARC). Other adverse events will be reviewed within the context of the earlier safety experience with the drug.

3.5 Exploratory Endpoints

To determine the effect(s) of adding ticagrelor for 30-days to participants with active RA after MTX failure on the following exploratory objectives:

- Soluble markers of inflammation, platelet and immune activation: IL-6, sCD14, hs-CRP, sCD40L, and sP-selectin, sCD163, and CXCL10/IP10.
- Intracellular cytokine concentration (TNF α and IL-6 from PBMCs)
- Contingent upon significant improvement in the primary objective and additional funding, measurements of inflammatory transcripts may be performed upon stored frozen PBMCs by measuring cell associated RNA and DNA.

4 Subject Selection and Withdrawal

